***Non-unique tables for AE\_TAB\_F\_X:***

Table 14.3.2.1 (AE\_TAC\_F\_X)

Summary of Treatment-Emergent Serious Adverse Events by System Organ Class and Preferred Term by Time Interval and Dose Group  
Population: Safety Analysis Set

AB\_F04  
AE\_F08  
AE\_F14  
AE\_F15  
AE\_F16

Listing Source: AE\_LAC\_F\_X

***Notes:***

- 1) ***AE\_TAC\_F\_X will be provided for each study part.***
- 2) ***Repeat AE\_TAB\_F\_X for Serious Adverse Events.***

Table 14.3.2.2 (AE\_TAL\_F\_X)

Summary of Treatment-Emergent Adverse Events of Special Interest by System Organ Class and Preferred Term by Time Interval and Dose Group  
Population: Safety Analysis Set

AB\_F04  
AE\_F08  
AE\_F14  
AE\_F15  
AE\_F16

Listing Source: AE\_LAL\_F\_X

***Notes:***

- 1) ***AE\_TAL\_F\_X will be provided for each study part.***
- 2) ***Repeat AE\_TAB\_F\_X for AESIS.***

Table 14.3.2.3 (AE\_TAE\_F\_X)

Summary of Treatment-Emergent Adverse Events Classified as Pulmonary Exacerbations by Preferred Term by Time Interval and Dose Group  
Population: Safety Analysis Set

Part: x		Time Interval: xx to xx			
Preferred Term	Type	MRT5005 Xmg	MRT5005 Xmg	MRT5005 Xmg	Pooled Placebo
		N=xx	N=xx	N=xx	N=xx
		n (%) m	n (%) m	n (%) m	n (%) m
Preferred Term 1					
All		xx (xx.x) xx	xx (xx.x) xx	xx (xx.x) xx	xx (xx.x) xx
Investigator-Defined		xx (xx.x) xx	xx (xx.x) xx	xx (xx.x) xx	xx (xx.x) xx
Protocol-Defined		xx (xx.x) xx	xx (xx.x) xx	xx (xx.x) xx	xx (xx.x) xx
Preferred Term 2					
All		xx (xx.x) xx	xx (xx.x) xx	xx (xx.x) xx	xx (xx.x) xx
Investigator-Defined		xx (xx.x) xx	xx (xx.x) xx	xx (xx.x) xx	xx (xx.x) xx
Protocol-Defined		xx (xx.x) xx	xx (xx.x) xx	xx (xx.x) xx	xx (xx.x) xx

AB\_F04  
AE\_F09  
AE\_F14a  
AE\_F15  
AE\_F16

Listing Source: AE\_LAF\_F\_X

**Notes:**

- 1) Repeat for each time interval. Time intervals for Part A are Overall, Study Day 1, 1 < Study Day  $\leq$  7, 1  $\leq$  Study Day  $\leq$  29, Study Day > 29. Time intervals for Part B are Overall, Study Day 1, 1 < Study Day  $\leq$  7, 1  $\leq$  Study Day  $\leq$  36, 1  $\leq$  Study Day  $\leq$  57, and Study Day > 57. Time intervals for Part D are Overall, Study Day 1, 1 < Study Day  $\leq$  5, 1  $\leq$  Study Day  $\leq$  11, 1  $\leq$  Study Day  $\leq$  32, and Study Day > 32.
- 2) In the column headers, report the number of subjects who were at risk for an AE at the start of the interval.
- 3) Report pulmonary exacerbations by type (all, investigator-defined and protocol-defined).
- 4) Sort Preferred Term by descending order of overall (MRT5005 + Placebo) frequency in subject counts.
- 5) The number of events will be summarized such that subjects with multiple TEAEs in a preferred term in a time interval in a type are counted more than once.

Table 14.3.1.3 (AE\_TAH\_F\_X)  
Number of Treatment-Emergent Adverse Events by Preferred Term by Dose Group  
Population: Safety Analysis Set

Part: x	MRT5005 Xmg N=xx Events	MRT5005 Xmg N=xx Events	MRT5005 Xmg N=xx Events	Pooled Placebo N=xx Events
Preferred Term 1	xx	xx	xx	xx
Preferred Term 2	xx	xx	xx	xx
Preferred Term 3	xx	xx	xx	xx
Etc.				

AB\_F04  
AE\_F09  
AE\_F14a  
AE\_F19

Listing Source: AE\_LAA\_F\_X

**Notes:**

- 1) Sort by descending order of overall (MRT5005 + Placebo) frequency.
- 2) Summarize number of events, so subjects with multiple TEAEs in preferred term in a time interval are counted more than once.

Table 14.3.1.3.1 (AE\_TAJ\_F\_A)  
Number of Treatment-Emergent Adverse Events by Preferred Term by Dose Group Through Day 29  
Population: Safety Analysis Set

Part: x	MRT5005 8mg N=xx Events	MRT5005 16mg N=xx Events	MRT5005 20mg N=xx Events	MRT5005 24mg N=xx Events	Pooled Placebo N=xx Events
Preferred Term 1	xx	xx	xx	xx	xx
Preferred Term 2	xx	xx	xx	xx	xx
Preferred Term 3	xx	xx	xx	xx	xx
Etc.					

AB\_F04  
AE\_F09  
AE\_F14a  
AE\_F19

Listing Source: AE\_LAA\_F\_A

**Notes:**

- 1) Sort by descending order of overall (MRT5005 + Placebo) frequency.
- 2) Summarize number of events, so subjects with multiple TEAEs in preferred term in a time interval are counted more than once.

Table 14.3.1.3.1 (AE\_TAJ\_F\_B)  
Number of Treatment-Emergent Adverse Events by Preferred Term by Dose Group Through Day 57  
Population: Safety Analysis Set

Part: x	MRT5005 8mg N=xx Events	MRT5005 12mg N=xx Events	MRT5005 16mg N=xx Events	MRT5005 20mg N=xx Events	Pooled Placebo N=xx Events
Preferred Term					
Preferred Term 1	xx	xx	xx	xx	xx
Preferred Term 2	xx	xx	xx	xx	xx
Preferred Term 3	xx	xx	xx	xx	xx
Etc.					

AB\_F04  
AE\_F09  
AE\_F14a  
AE\_F19

Listing Source: AE\_LAA\_F\_B

**Notes:**

- 1) Sort by descending order of overall (MRT5005 + Placebo) frequency.
- 2) Summarize number of events, so subjects with multiple TEAEs in preferred term in a time interval are counted more than once.

Table 14.3.1.3.1 (AE\_TAJ\_F\_D)  
Number of Treatment-Emergent Adverse Events by Preferred Term by Dose Group Through Day 32  
Population: Safety Analysis Set

Part: x	MRT5005 4mg N=xx Events	Placebo N=xx Events
Preferred Term		
Preferred Term 1	xx	xx
Preferred Term 2	xx	xx
Preferred Term 3	xx	xx
Etc.		

AB\_F04

AE\_F09  
AE\_F14a  
AE\_F19

Listing Source: AE\_LAA\_F\_D

**Notes:**

- 1) Sort by descending order of overall (MRT5005 + Placebo) frequency.
- 2) Summarize number of events, so subjects with multiple TEAEs in preferred term in a time interval are counted more than once.

Table 14.3.1.4 (AE\_TAN\_F\_O)  
Number of Treatment-Emergent Adverse Events by Preferred Term and Time Interval  
Population: Safety Analysis Set

Part: x Time Interval: x	Pooled MRT5005 N=xx Events	Pooled Placebo N=xx Events
Preferred Term		
Preferred Term 1	xx	xx
Preferred Term 2	xx	xx
Preferred Term 3	xx	xx
Etc.		

AB\_F04  
AE\_F09  
AE\_F14a  
AE\_F19  
AE\_F18

**Notes:**

- 1) The first page will be "Part: All Study Parts" with "Time Interval: Overall" and will include all AEs across all study parts. The subsequent page will be: "Part: All Study Parts" with "Time Interval: 1 month post-dose"
- 2) In the column headers, report the number of subjects who were at risk for an AE at the start of the interval.
- 3) Sort by descending order of overall (Pooled MRT5005 + Pooled Placebo) frequency.
- 4) Summarize number of events, so subjects with multiple TEAEs in preferred term in a time interval are counted more than once.

Table 14.3.2.4 (AE\_TAM\_F\_X)

Summary of Treatment-Emergent Febrile Reactions in First 24 Hours After Completion of Nebulization by Preferred Term and Dose Group  
Population: Safety Analysis Set

	MRT5005 Xmg N=xx n (%)	MRT5005 Xmg N=xx n (%)	MRT5005 Xmg N=xx n (%)	Pooled Placebo N=xx n (%)
Number of Febrile Reactions Reported	xx	xx	xx	xx
Number of Subjects with Any Febrile Reactions Reported [1]	xx (xx.x)	xx (xx.x)	xx (xx.x)	xx (xx.x)
Number of Febrile Reactions by Severity [2]				
Mild	xx	xx	xx	xx
Moderate	xx	xx	xx	xx
Severe	xx	xx	xx	xx
Number of Subjects with Febrile Reactions by Maximum Severity [3]				
Mild	xx (xx.x)	xx (xx.x)	xx (xx.x)	xx (xx.x)
Moderate	xx (xx.x)	xx (xx.x)	xx (xx.x)	xx (xx.x)
Severe	xx (xx.x)	xx (xx.x)	xx (xx.x)	xx (xx.x)

[1] AE\_F05

[2] AE\_F17c

[3] AE\_F07a

Note: AE\_F17a

Listing Source: AE\_LAK\_F\_X

**Notes:**

1) **AE\_TAM\_F\_X** will be produced for each study part.

Table 14.3.2.6 (AE\_TAP\_F\_X)  
Summary of Treatment-Emergent Hypersensitivity Reactions in First 24 Hours After Completion of Nebulization by Preferred Term and Dose Group  
Population: Safety Analysis Set

	MRT5005 Xmg N=xx n (%)	MRT5005 Xmg N=xx n (%)	MRT5005 Xmg N=xx n (%)	Pooled Placebo N=xx n (%)
Number of Hypersensitivity Reactions Reported	xx	xx	xx	xx
Number of Subjects with Any Hypersensitivity Reactions Reported [1]	xx (xx.x)	xx (xx.x)	xx (xx.x)	xx (xx.x)
Number of Hypersensitivity Reactions by Severity				
Mild	xx	xx	xx	xx
Moderate	xx	xx	xx	xx
Severe	xx	xx	xx	xx
Number of Subjects with Hypersensitivity Reactions by Maximum Severity [2]				
Mild	xx (xx.x)	xx (xx.x)	xx (xx.x)	xx (xx.x)
Moderate	xx (xx.x)	xx (xx.x)	xx (xx.x)	xx (xx.x)
Severe	xx (xx.x)	xx (xx.x)	xx (xx.x)	xx (xx.x)

[1] AE\_F05

[2] AE\_F07b

Note: AE\_F17b

Listing Source: AE\_LAK\_F\_X

**Notes:**

1) **AE\_TAM\_F\_X** will be produced for each study part.

Table 14.3.2.5 (AE\_TAO\_F\_O)  
Summary of Treatment-Emergent Febrile Reactions in First 24 Hours After Completion of Nebulization by Preferred Term  
Population: Safety Analysis Set

	Pooled MRT5005 N=xx n (%)	Pooled Placebo N=xx n (%)
Number of Febrile Reactions Reported	xx	xx
Number of Subjects with Any Febrile Reactions Reported [1]	xx (xx.x)	xx (xx.x)
Number of Febrile Reactions by Severity [2]		
Mild	xx	xx
Moderate	xx	xx
Severe	xx	xx
Number of Subjects with Febrile Reactions by Maximum Severity [3]		
Mild	xx (xx.x)	xx (xx.x)
Moderate	xx (xx.x)	xx (xx.x)
Severe	xx (xx.x)	xx (xx.x)

[1] AE\_F05

[2] AE\_F17c

[3] AE\_F07a

Note: AE\_F17a

Listing Source: AE\_LAK\_F\_X

Table 14.3.2.7 (AE\_TAO\_F\_O)  
Summary of Treatment-Emergent Hypersensitivity Reactions in First 24 Hours After Completion of Nebulization by Preferred Term  
Population: Safety Analysis Set

	Pooled MRT5005 N=xx n (%)	Pooled Placebo N=xx n (%)
Number of Hypersensitivity Reactions Reported	xx	xx
Number of Subjects with Any Hypersensitivity Reactions Reported [1]	xx (xx.x)	xx (xx.x)
Number of Hypersensitivity Reactions by Severity		
Mild	xx	xx
Moderate	xx	xx
Severe	xx	xx
Number of Subjects with Hypersensitivity Reactions by Maximum Severity [2]		
Mild	xx (xx.x)	xx (xx.x)
Moderate	xx (xx.x)	xx (xx.x)
Severe	xx (xx.x)	xx (xx.x)

[1] AE\_F05

[2] AE\_F07b

Note: AE\_F17b

Listing Source: AE\_LAK\_F\_X

## Vital Signs

Table 14.3.5.1 (VS\_TAA\_F\_X)  
Mean and Mean Change from Baseline in Vital Signs by Visit and Dose Group  
Population: Safety Analysis Set

Part: x																
Parameter (unit)	MRT5005 Xmg		MRT5005 Xmg		MRT5005 Xmg		Pooled Placebo									
	Visit Statistic	N=xx	Absolute Change from Baseline	Actual	Absolute Change from Baseline	Actual	Absolute Change from Baseline	Actual								
Parameter 1 (unit)																
Baseline																
Subject 1	xx		xx		xx		xx									
Subject 2	xx		xx		xx		xx									
Subject 3	xx		xx		xx		xx									
Subject 4	xx		xx		xx		xx									
Mean	xx.x		xx.x		xx.x		xx.x									
SD	xx.xx		xx.xx		xx.xx		xx.xx									
DAY 1 (0HRPOST-DOSE)																
Subject 1	xx	xx	xx	xx	xx	xx	xx	xx								
Subject 2	xx	xx	xx	xx	xx	xx	xx	xx								
Subject 3	xx	xx	xx	xx	xx	xx	xx	xx								
Subject 4	xx	xx	xx	xx	xx	xx	xx	xx								
Mean	xx.x	xx.x	xx.x	xx.x	xx.x	xx.x	xx.x	xx.x								
SD	xx.xx	xx.xx	xx.xx	xx.xx	xx.xx	xx.xx	xx.xx	xx.xx								
Etc.																
AB_F01a																
BL_F01																
CH_F01																
VS_F01 (for Parts A and B)																

Listing Source: VS\_LAA\_F\_X

**Notes:**

- 1) *Parameters include: Systolic Blood Pressure, Diastolic Blood Pressure, Pulse Rate, Respiratory Rate, Temperature, Height, Weight, BMI, Pulse Oximetry.*
- 2) *Include all post-baseline visits/timepoints where vital signs are collected for Systolic Blood Pressure, Diastolic Blood Pressure, Pulse Rate, Respiratory Rate, Temperature, Weight, Pulse Oximetry.*
- 3) *For any parameter collected multiple times during the nebulization period, select the latest 'DOSING' record for that dosing day.*
- 4) *Include baseline only for Height and BMI.*
- 5) *Exclude Part A Day 1 (Dosing) records.*

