- h Blood pressure and pulse rate will be monitored continuously during nebulization of IP (except during rest periods), and will be recorded at the end of nebulization with each of the multiple nebulizers used to deliver the total volume of IP (eg, for the 16 mg dose, blood pressure and pulse rate will be recorded at the end of nebulization with each of the 4 nebulizers used to deliver the 28 mL total volume); the final recording will count as the Hour 0 time point. Blood pressure or pulse rate may be recorded more frequently, if clinically indicated. (Body temperature will not be monitored during the dosing period.)
- i Oxygen saturation, measured by pulse oximetry, will be monitored continuously during nebulization of IP, and will be recorded at the end of nebulization with each of the multiple nebulizers used to deliver the total volume of IP (see footnote h for example); the final recording will count as the Hour 0 time point. Oxygen saturation may be recorded more frequently, if clinically indicated.
- j All body mass index calculations will use the subject's height measured at the initial screening visit.
- k A serum or urine β -hCG pregnancy test will be performed on all female subjects, regardless of childbearing potential, at the initial screening visit and on Day -1
- l If feasible for the subject, all spirometry testing should be performed "pre-bronchodilator" if the subject is receiving treatment with a short-acting bronchodilator (Section 7.5.2.12). The spirometry testing at the 8-hour time point on Day 1 has an expanded window of ± 1 hour to accommodate this. If a subject experiences respiratory distress or pulmonary symptoms, at the discretion of the Investigator, unscheduled spirometry testing may be performed when the subject is stable.
- m Chest x-rays will consist of routine posterioranterior and lateral views. The baseline chest x-ray can be performed at any time from Day -14 to Day -2 during the screening period.
- n Assays will measure antibody and T cell responses to CFTR protein as well as anti-PEG antibodies.
- o In addition to the time points specified in the schedule of assessments, ad hoc testing for immune response assays and/or [REDACTED] mRNA and [REDACTED] assays may also be performed when immunogenicity is suspected, such as febrile and/or allergy/hypersensitivity events or unexplained bronchospasm.

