- g Blood pressure and pulse rate will be monitored continuously during nebulization of IP (except during rest periods), and will be recorded at the end of nebulization with each of the multiple nebulizers used to deliver the volume of IP (eg, for the 16 mg dose, blood pressure and pulse rate will be recorded at the end of nebulization with each of the 4 nebulizers used to deliver the 28 mL total volume); the final recording will count as the Hour 0 time point. Blood pressure or pulse rate may be recorded more frequently, if clinically indicated. (Body temperature will not be monitored during the dosing period).
- h Oxygen saturation, measured by pulse oximetry, will be monitored continuously during nebulization of IP (except during rest periods), and will be recorded at the end of nebulization with each of the multiple nebulizers used to deliver the total volume of IP (see footnote g for example); the final recording will count as the Hour 0 time point. Oxygen saturation may be recorded more frequently, if clinically indicated.
- i If feasible for the subject, spirometry testing should be performed "pre-bronchodilator" if the subject is receiving treatment with a short-acting bronchodilator (Section 7.5.2.12). The spirometry testing at the 6-hour time point has an expanded window of ± 1 hour to accommodate this.
- j The Day 1 pre-dose ECG and spirometry must be reviewed prior to the first dose. The administration of IP should optimally occur within 2-3 hours after subjects have completed their routine pulmonary therapies (airway clearance and pulmonary medications) for the day. For subjects whose pulmonary medications do not include an inhaled short-acting beta-agonist (or it is not given within the 2-3 hour window prior to IP administration), albuterol (2 to 4 puffs) will be administered approximately 20 minutes before treatment with IP. IP will be administered by the respiratory route using an InnoSpire Go nebulizer. Depending on the dose level, nebulization times will range from approximately 44 to 133 minutes. During nebulization of IP, the subject should be monitored closely for any signs or symptoms of respiratory distress (eg, dyspnea, wheezing, bronchospasm).

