6.2.2.1. Dosing of IP

The administration of IP will be performed by a blinded, qualified member of the study staff. For scheduling of IP administration with respect to the subjects' routine pulmonary medications and therapies, refer to Section [5.1.1.1](#).

For administration of the IP, the subject should be seated comfortably in a chair and the nebulizer should be held in an upright position; the arm holding the nebulizer may be supported according to the subject's preference (eg, resting the elbow on the arm of a phlebotomy chair). The subject will be instructed to place the mouthpiece of the nebulizer between their teeth, with their lips firmly sealed around the mouthpiece, and to breathe through their mouth at their normal rate and tidal volume until the aerosol formation completely stops (see instruction manual for InnoSpire Go micropump nebulizer in [Appendix 3](#)). The subject should turn off the nebulizer when taking the mouthpiece out of their mouth (eg, to talk) to avoid loss of IP and to minimize secondary exposure (see below). As described above, multiple nebulizers may be used to deliver IP ([Table 11](#)); to reduce the burden of administration, the subject will be offered a 15 to 20-minute rest period before changing to the next nebulizer (if applicable; this interval may be extended if needed for subject tolerability). For example, subjects receiving the 16 mg dose level may have rest periods after the first, second, and third nebulizers for a total of 3 rest periods during the nebulization.

During nebulization of IP, the subject will be monitored closely for any signs or symptoms of respiratory distress (eg, dyspnea, wheezing, bronchospasm). In Part A and Part B, blood pressure, pulse rate, and oxygen saturation measured by pulse oximetry will be continuously monitored during nebulization (except during rest periods) and will be recorded at the end of the nebulization with each of the multiple nebulizers used to deliver the total volume of IP (eg, for the 16 mg dose, values will be recorded at the end of the nebulization with each of the 4 nebulizers used to deliver the 28 mL of total volume); the final recording will count as the Hour 0 time point. Blood pressure, pulse rate, and/or oxygen saturation may be recorded more frequently, if clinically indicated. Body temperature will not be monitored during the dosing period.

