During the nebulization of IP in Parts A and B only, blood pressure and pulse rate will be monitored continuously (except during rest periods) with measurements to be recorded every 5 minutes (8 mg dose level) or 10 minutes (12, 16, 20, and 24 mg dose levels), or more frequently if clinically indicated. Any changes from baseline that are deemed clinically significant by the Investigator are to be recorded as an AE.

Body Temperature

Oral temperature should be taken by placing a digital thermometer under the tongue for at least 10 seconds and the temperature reported in degrees Celsius. Other methods to measure the subject's temperature must be approved by the Sponsor.

Respiratory Rate

The respiratory rate should be taken when the subject is at rest in a comfortable position. The observer should hold the extremity of the subject as a distraction for the subject (ie, pretending he/she is taking the subject's radial pulse) and count the number of respirations for 30 seconds. The respiratory rate is reported as the number of breaths per minute.

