AE	Definition	AE_F17a	Note:	Febrile reactions were identified based on a preferred term of body temperature increased or preferred term of pyrexia within the 24 hours after completion of nebulization on any dosing day with at least one other systemic symptom reported as a preferred term of headache, arthralgia, myalgia, fatigue, chills, nausea, or vomiting within the 24 hours after completion of nebulization on any dosing day.
AE	Definition	AE_F17b	Note:	Hypersensitivity reactions were identified based on a preferred term of hypersensitivity within the 24 hours after completion of nebulization on any dosing day.
AE	Definition	AE_F17c	[2]	Severity grade for each febrile reaction was based on the maximum severity of the preferred terms comprising the febrile reaction. Febrile reactions with missing severity were counted as Severe.

Data Type	Footnote Type	Code	Prefix	Footnote
AE	Interval	AE_F18	Note:	The 1 month post-dose time interval is defined as through Day 29 for Part A, through Day 57 for Part B, through Day 32 for Part D.
AE	Count	AE_F19	Note:	N represents the number of subjects in a given dose group that experienced an adverse event.
EG	Baseline	EG_F01	Note:	The baseline value was defined as the Day -1 ECG measurement.
EG	Baseline	EG_F01D	Note:	The baseline value was defined as the screening ECG measurement.
EG	Schedule	EG_F02	Note:	Only ECGs scheduled per the protocol were summarized.
EX	Count	EX_F01	Note:	Full dose refers to completion of all nebulizers as planned; partial dose refers to incomplete nebulization. Full and partial dose are independent of the presence or absence of excess residual in the medication chamber.
VS	Schedule	VS_F01	Note:	The final recording during nebulization for blood pressure, pulse rate, and pulse oximetry was counted as the 'DAY 1 (0 HR POST-DOSE)' value.
RE	Baseline	RE_F01	[1], [3]	The baseline value was defined as the average of the results from testing on Day -1 and at pre-dose on Day 1.
RE	Baseline	RE_F01D	[1], [3]	The baseline value was defined as the result from testing pre-dose on Day 1.
RE	Baseline	RE_F01O	[1], [3]	The baseline value was defined as the average of the results from testing on Day -1 and at pre-dose on Day 1 for Part A and Part B, and defined as the result from testing pre-dose on Day 1 for Part D.
CFQ	Baseline	CFQ_F01	Note:	The baseline value was defined as the Day -1 CFQ-R respiratory domain score.

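### Table 14.3.5.1 keeps only the final nebulization reading of blood pressure, pulse and SpO2, so a transient change not reported as an AE appears in no summary table; two recording rules need reconciling

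*SAP*

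**What the plan says.** **SAP, Table 14.3.5.1 specification.** Note 3: "For any parameter collected multiple times during the nebulization period, select the latest 'DOSING' record for that dosing day". Note 5: "Exclude Part A Day 1 (Dosing) records". Footnote VS_F01, attached for Parts A and B: "The final recording during nebulization for blood pressure, pulse rate, and pulse oximetry was counted as the 'DAY 1 (0 HR POST-DOSE)' value".

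**Basis in the protocol.** Section 6.2.2.1 and the footnotes to Tables 1 and 7 state that "the final recording will count as the Hour 0 time point".

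**How often readings are recorded.** Sections 7.5.2.4 (blood pressure, pulse rate) and 7.5.2.5 (pulse oximetry) call for continuous monitoring in Parts A and B "with measurements to be recorded every 5 minutes (8 mg dose level) or 10 minutes" at the four higher dose levels. Section 6.2.2.1 says values "will be recorded at the end of the nebulization with each of the multiple nebulizers used to deliver the total volume of IP", and the Table 1 and Table 7 footnotes say the same. Neither set of passages refers to the other.

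**Other routes into the report.** Protocol 7.5.2.4 and 7.5.2.5 require a change from baseline that the Investigator considers clinically significant to be recorded as an AE. SAP 9.6.1 plans a listing of vital sign results.

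**Status of these measures.** Vital signs and oxygen saturation are components of the primary endpoint (Protocol 2.4.1, SAP 2.2.1).

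**The concern.** The product is inhaled over a planned 44 to 133 minutes in Parts A and B, and the protocol treats an acute airway response as a real possibility. Section 5.1.1.1 has albuterol given beforehand, where no short-acting beta-agonist was taken in the preceding window, to limit bronchoconstriction. Section 8.1.8.1 names bronchospasm within the AESI. Continuous monitoring is required over exactly this window, yet the only numeric by-dose summary shows its end point alone.

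The AE route depends on a judgement for which these sections give no numeric threshold, and the AE tables carry no SpO2, pulse or pressure values. With three active subjects planned per dose group, a short-lived pattern of modest falls at higher doses could be recorded and still not be visible in any comparison with placebo.

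**Working it through.** **1. Which displays could show a dosing-period extreme?** SAP Sections 14 and 15 plan one vital-signs table (14.3.5.1) and one set of vital-sign figures (14.3.5.1.1). The figures plot body temperature, which Protocol 6.2.2.1 says is not monitored during dosing. No display gives a minimum, a worst change or a threshold count during nebulization.

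**2. Check of the input times.** Protocol Table 11 gives nebulization times and nebulizer numbers. Time should equal dose / concentration / flow, with 0.6 mg/mL and 0.3 mL/min. For 8 mg, 8 / 0.6 / 0.3 = 44.4 min against the stated 44. For 12, 16, 20 and 24 mg the results are 66.7, 88.9, 111.1 and 133.3 min against 66, 89, 110 and 133. Agreement is within about 1%, so the stated times are used.

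**3. Readings per dosing session.** Interval rule: whole intervals in the stated time, 5 minutes at 8 mg and 10 minutes otherwise. End-of-nebulizer rule: number of nebulizers.

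| Dose (mg) | Interval rule | End-of-nebulizer rule | Ratio | Share tabulated (interval / nebulizer) |
|---|---|---|---|---|
| 8 | 44/5 = 8.8, so 8 | 2 | 4.0 | 12.5% / 50.0% |
| 12 | 66/10 = 6.6, so 6 | 3 | 2.0 | 16.7% / 33.3% |
| 16 | 89/10 = 8.9, so 8 | 4 | 2.0 | 12.5% / 25.0% |
| 20 | 110/10 = 11 | 5 | 2.2 | 9.1% / 20.0% |
| 24 | 133/10 = 13.3, so 13 | 6 | 2.2 | 7.7% / 16.7% |

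The 12 mg level is in Part B only and 24 mg in Part A only, so the longest Part B session is 110 minutes.

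**4. What the selection implies.** The last recorded SpO2 cannot be lower than the lowest recorded SpO2. The fall shown at Hour 0 therefore equals or understates the largest recorded fall. The documents give no data from which to estimate the size of that difference.

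**5. Why a bare minimum would not be enough.** An extreme over more readings is larger by chance. If readings were independent and normal (an assumption, for illustration), the expected minimum would be about 0.56 SD below the mean for 2 readings and 1.27 SD below for 6. The difference, 1.27 - 0.56 = 0.71 SD, could appear between 8 mg and 24 mg with no drug effect. Successive readings in one subject are likely to be correlated, which would shrink this. Placebo sessions match their dose group in volume, time and nebulizers (Protocol 6.2.2), so pooled placebo mixes these counts.

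**The case against.** Much of the opposing case stands.

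- **Such a change might be thought to reach no table at all.** The documents do not support that. A clinically significant change is recorded as an AE and enters the AE tables by time interval, including Study Day 1. AEs during nebulization are also listed separately (Listing 16.2.7.8).
- **The SAP might be thought to depart from the protocol.** It does not: taking the final recording as Hour 0 is the protocol's own rule.
- **Note 5 might be read as discarding all Part A dosing data.** With VS_F01, it is better read as avoiding duplication, provided the final reading is also stored as a 0 HR record.
- **The last reading might be thought to follow a recovery period, biasing the table towards no effect.** Section 6.2.2.1 places the offered rests before a change to the next nebulizer, so none is scheduled after the last. The final reading comes at full cumulative dose and is followed by tabulated readings at 0.5, 1, 2, 4 and 6 hours, and at 8 hours in Part A. Only the bound in step 4 of the working is established.
- **The two recording rules might be called incompatible.** A site could follow both, and both allow more frequent recording. What stands is that they are not cross-referenced, so sites may have collected different amounts of data.

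With groups this small, a subject-level listing can also reveal a nadir. That is fair, but a listing does not set dose groups beside placebo. The shell of Listing 16.2.9.1 is not legible in the copy available, so its inclusion of every dosing reading is assumed rather than confirmed.

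**Conclusion.** The point holds in limited form, for Parts A and B and for blood pressure, pulse rate and SpO2. A transient change during dosing that recovers by the final reading and is not judged clinically significant appears in no summary table, and at most in a listing. At most one reading per session is tabulated: 1 of 6 to 1 of 13 under the interval rule, or 1 of 2 to 1 of 6 under the end-of-nebulizer rule. The two rules differ 2- to 4-fold in readings collected.

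These counts assume completed nebulization at the stated times, which the protocol calls targets, with no extra readings. They do not show that any signal was missed or that the Hour 0 row is wrong. This is a worthwhile, inexpensive addition and a protocol clarification.

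**What to change.** 1. Keep the Hour 0 row in Table 14.3.5.1.
2. For Parts A and B, add by dosing day and dose group each subject's lowest SpO2 during nebulization and largest change from pre-dose in pulse rate and systolic pressure. Print the number of readings behind each value, and identify each placebo subject's matched dose group. The shell already shows individual values.
3. Compare doses only against the reading count, or restrict the comparison to the end-of-nebulizer readings that the groups share. The first two exist at every Part A and B dose level when nebulization is completed; the price is losing later readings at higher doses.
4. Extend VS_F01 beyond Day 1, since Part B doses on five days, and confirm that the Part A final reading is held as a 0 HR record.
5. Reconcile Protocol 7.5.2.4 and 7.5.2.5 with 6.2.2.1 and the Table 1 and Table 7 footnotes. No particular interval is proposed here. New wording cannot change data already collected, so the reading counts in item 2 are needed in any case.

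The cost is a few derived variables and table rows from data already recorded, plus protocol wording.
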